Protocol Title:
Treating Bacterial Overgrowth in Parkinson's Disease

Principle Investigator: [name]
Co-Investigator: [name]

Amendment 3

HYPOTHESIS AND SPECIFIC AIMS

Parkinson's disease (PD) is a progressive neurodegenerative disorder that includes motor and non-motor impairment, including gastrointestinal (GI) dysfunction, one of the earliest abnormalities. The GI dysfunction is expressed as reduction of intestinal motility, which puts PD patients at risk for developing small intestinal bacterial overgrowth (SIBO), which develops in about 50% of PD patients, compared to only 8-20% of healthy age-matched controls[1, 2]. SIBO-positive PD patients have poorer response to therapy and more motor fluctuations than non-SIBO PD patients. Finally, open-label data suggest that the antibiotic rifaximin leads to eradication of SIBO and improvement in motor control in affected PD patients.

Here we propose to collect pilot data that would support the submission of a U01 application to the NIH for a large randomized controlled trial investigating the effect of SIBO eradication on reducing motor complications in PD patients. **Our central hypothesis is that SIBO-positive PD patients treated with rifaximin will exhibit an improvement in motor fluctuations as measured by a decrease in daily “off” time.**

Primary endpoints: to determine the change in “off” time after rifaximin treatment as measured by both patient report (the Hauser PD diary) and an objective monitoring system (Kinesia 360). “Off” time will be compared using a between-subjects analysis (rifaximin versus placebo), as well as a within-subjects analysis comparing each subject's baseline to 1 and 3 months post-rifaximin treatment. Examining 2 post-treatment time points will provide an estimate for the optimal time point for the primary outcome measure as well as for treatment duration in a future study.

Secondary endpoints:

1. **to investigate whether the treatment effect of rifaximin varies by method of SIBO detection.** We propose to use two non-invasive methods of SIBO detection, serum unconjugated bile acids versus a combination of lactulose and glucose breath tests. Thus, we can determine if there is a differential treatment effect based on method of detection, and use these data to select the detection method for a larger, randomized trial.

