2. **To compare outcomes of the Hauser diary versus the Kinesia 360 monitoring system.** Within-patient results will be compared for sensitivity and effect size, and these data will be used to select the primary endpoint for a larger, randomized trial.

Tertiary endpoints:

1. Change in daily “on” time with no dyskinesia and without troublesome dyskinesia.
2. Change in daily “on” time with troublesome dyskinesia
3. Change in motor subscale (part III) of the Movement Disorders Society-Unified Parkinson's Disease Rating Scale (MDS-UPDRS)
4. Change in the complication of therapy subscale (Part IV) scores of the MDS-UPDRS
5. Presence/recurrence of SIBO 1 month post-treatment
6. Correlation between the treatment effect of rifaximin (change in “off” time) and SIBO eradication as measured by both non-invasive methods of SIBO detection.
7. Change in Patient Global Impression of Change (PGI-C).

The current proposal is designed to demonstrate our ability to detect and treat SIBO in PD patients with motor fluctuations, to estimate the effect size and standard deviation of motor improvements, and to inform selection of the best SIBO detection method. In addition, it will help us determine the optimal timeline for assessing motor endpoints, and estimate the duration of benefits after treatment.

BACKGROUND AND SIGNIFICANCE

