Study Plan: PD patients with motor fluctuations (≥ 4 hours of self-reported "off" time per day) will be screened for SIBO using breath tests (LBT and GBT). Subjects testing positive by either method will be eligible for enrollment, whereas those testing negative by *both* methods will be considered screen failures, and will be discontinued from the study. We expect that approximately 50% of screened patients will be SIBO-positive [1, 2]; therefore we plan to screen 48 subjects to achieve an enrollment of 24. SIBO-positive subjects will be asked to return for a baseline visit 2-4 weeks after screening, and to complete the standardized Hauser diary[16, 17] capturing daily "on" and "off" time for 3 days prior to the baseline visit. Daily "off" time must average at least 4 hours per day to proceed with enrollment. They will also use the Kinesia 360 monitoring system during this time.

Subjects meeting all inclusion/exclusion criteria will be enrolled and randomly assigned to one of two groups in a randomized, double-blind, crossover fashion (see Figure), each treated with a one-week course of the antibiotic rifaximin as well as a one-week course of matching placebo. Group A will receive rifaximin at baseline and placebo at 3 months, whereas group B will receive placebo at baseline and

rifaximin at 3 months. Outcome measures including motor control will be assessed at the following time points: baseline (BL, pre-treatment), 1 month, 3 months, 4 months, and 6 months.

Clinical assessments will include a motor examination and evaluation of motor complications using sections III and IV of the MDS-UPDRS, respectively. Patients will be trained in the correct use of the PD Hauser diary to log “on” and “off” time, as described below.

Blinding: Amendment 3 modifies this study to be a fully double-blind crossover, such that neither participants nor researchers will know when the subject receives rifaximin or placebo. This will be explained to the participants, so they will know that they will receive one treatment course of each during the study, but they will not know in which order they were treated. The results of the breath tests (SIBO-positive or SIBO-negative) will only be revealed to the subject at screening, which determines their ability to enroll in the study. The results of subsequent breath tests on enrolled subjects will not be revealed to subjects or the motor assessor to avoid bias on symptomatic outcome measures.

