Our primary outcome, change in “off” time, will be analyzed using two separate analyses. A within-subjects comparison (paired t-test) will compare all subjects (n=24) before and after rifaximin treatment, whereas a between-subjects analysis (two-sample t-test) will compare placebo treatment (n=12) to rifaximin treatment (n=12). Therefore, we will have one analysis with greater power to detect a treatment effect, and a second analysis with greater validity for designing a future placebo-controlled trial.

Based on previous data, we have estimated that SIBO-positive PD patients have 5.1 hours of “off” time, with a treatment effect of rifaximin to decrease “off” time by 2 hours. Standard deviation is estimated to be approximately 1.5 to 2 hours [2].

Because all subjects will ultimately receive rifaximin treatment, a within-subjects analysis will compare all 24 subjects before and (1 and 3 months) after treatment using paired t-tests. For group A, this corresponds to baseline versus 1 month, and baseline versus 3 months. For group B, this corresponds to 3 months (end of placebo treatment, and baseline for rifaximin treatment) versus 4 months, and 3 months versus 6 months. Assuming a mean “off” time before treatment of 5.1 hours, a conservative estimate of standard deviation of 2.5 hours, and a moderate correlation of 0.7 between the measurements before and after treatment, we will have 99.8% power to detect a difference of 2 hours, and 95.3% power to detect a difference of 1.5 hours of “off” time.

A second analysis will compare placebo treatment versus rifaximin treatment between subjects. We will use a two-sample t-test to compare the “off” time between groups A and B at 1 month and 3 months past baseline. Assuming initial “off” time in both groups to be 5.1 hours, a decrease in “off” time of 2 hours in the rifaximin group, and no change in the placebo group, we will have 87.7% power or 64.9% power to detect the difference between groups based on standard deviations of 1.5 and 2.0 hours, respectively. Due to the nature of this pilot study, and the imprecise estimates of standard deviation, it is possible that this analysis will not have the power to detect a treatment difference between groups. However, these data will provide valuable estimates of mean and standard deviation which can be used

to design a larger clinical trial. Furthermore, the within-subjects analysis described above should have ample power to detect a treatment effect.

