Setting: Study visits will take place at the [name].

HUMAN SUBJECTS

Consecutive consenting patients will be recruited from the University of Cincinnati Movement Disorders Center. We expect to screen 4-5 patients per month, and to complete enrollment in one year (48 screened, 24 enrolled). Assessments will be ongoing for an additional 6 months.

Inclusion criteria:

1. Diagnosis of PD according to the UK Brain Bank criteria[18]
2. Daily “off” time ≥ 4 hours according to subject-completed Hauser diary.
3. No changes in levodopa or any other dopaminergic medications will be expected during the course of the study, at the judgment of the treating clinician.
4. Montreal Cognitive Assessment (MoCA) ≥ 24 .
5. Age 18 and older.

Exclusion criteria:

1. Any comorbid non-PD-associated gastrointestinal (e.g., achlorhydria) or systemic disease that may alter absorption or confound the study results, including immune disease.

2. Concurrent exposure to immunosuppressive drugs or antibiotic treatment, or within 30 days of screening.
3. Known allergy to rifaximin
4. Women who are pregnant, lactating, or plan to become pregnant.

Risk/Benefits: This study involves more than minimal risk due to use of study drug and the breath tests (which involve ingestion of sugar). The risks associated with Rifaximin treatment are similar to placebo, and include flatulence, headache, abdominal pain, rectal tenesmus, defecation urgency, nausea, constipation, pyrexia, and vomiting. The risks associated with breath testing are related to the possibility of poor digestion and absorption of carbohydrates, and may include bloating, distention, pain, diarrhea, and hypoglycemia. These risks are similar to what participants would experience any time they would take an antibiotic or ingest a moderate amount of carbohydrate.

Withholding PD medications for the MDS-UPDRS On/off evaluation may cause a temporary worsening in PD symptoms including tremor, bradykinesia, rigidity, freezing, and other PD-associated symptoms.

There are no controlled data regarding the use of Rifaximin during pregnancy or lactation, and it is not known whether Rifaximin is excreted in breastmilk. Subjects may not participate if they are pregnant, lactating, or plan to become pregnant or cause a pregnancy. Subjects will be counseled on birth control methods.

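### Secondary endpoint 2 chooses between diary and Kinesia 360 on within-patient effect size; the only such contrast defined is uncontrolled and, through the diary entry gate, tilts modestly towards the diary

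*Combined protocol and SAP*

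**What the plan says.** Under Hypothesis and Specific Aims, the primary endpoint is the change in off time "as measured by both patient report (the Hauser PD diary) and an objective monitoring system (Kinesia 360"). It is analysed between subjects and also in a "within-subjects analysis comparing each subject's baseline to 1 and 3 months post-rifaximin treatment". Secondary endpoint 2 then compares the two instruments: "Within-patient results will be compared for sensitivity and effect size, and these data will be used to select the primary endpoint" for the larger trial. Neither sensitivity nor effect size is defined, and the statistical analysis plan section gives no method for this endpoint.

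That section does define the within-subject pairs. "For group A, this corresponds to baseline versus 1 month, and baseline versus 3 months". For Group B the first pair is "3 months (end of placebo treatment, and baseline for rifaximin treatment) versus 4 months", and the second is 3 months versus 6 months.

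On entry, the Study Plan requires that daily off "time must average at least 4 hours per day to proceed with enrollment", measured on the three-day diary completed before the baseline visit. Inclusion criterion 2 repeats it: off "time ≥ 4 hours according to subject-completed Hauser diary". Of Kinesia the Study Plan says only: "They will also use the Kinesia 360 monitoring system during this time". It has no threshold.

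**The concern.** The diary that admits a patient is also Group A's before value. Patients whose diary happened to read high that week are over-represented, so the diary mean should fall at the next visit whatever the treatment. Kinesia is worn on the same days but is not selected on. Its baseline is raised only through its correlation with the diary, and it falls back less or not at all.

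A second mechanism runs the same way. The protocol contrasts the diary as patient report with Kinesia as objective, and participants know that they will receive one course of each treatment. Blinding balances expectation between arms but does not remove it from a before-after change.

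This is a different question from whether the paired t-test shows a drug effect. Here the bias differs between the instruments and feeds into which one becomes the primary endpoint of a placebo-controlled trial.

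**Working it through.** **Inputs from the statistical analysis plan section.** Mean off time 5.1 h; SD 2.5 h (within-subjects power) or 1.5 to 2.0 h (between-subjects power); before-after correlation 0.7; 24 patients, 12 per group. The gate of 4 h comes from the Study Plan and inclusion criterion 2.

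**The plan's own figures.** SD of change = 2.5 × √(2 × (1 − 0.7)) = 1.936 h. A paired t-test with n = 24 at two-sided 0.05 (alpha is not stated; this value is assumed) has power 99.8% for 2 h and 95.3% for 1.5 h. The two-sample test at 12 per group gives 87.7% (SD 1.5 h) and 64.9% (SD 2.0 h). All four stated powers reproduce. The issue is the selection criterion, not the power.

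**Fall in the diary caused by the gate (normal model).**
- Standardised cut: (4 − 5.1)/2.5 = −0.44. About 67% of patients pass, and the inverse Mills ratio is λ = 0.540.
- Gated diary mean: 5.1 + 2.5 × 0.540 = 6.45 h.
- Expected diary mean at the next visit with no effect: 5.1 + 0.7 × 1.35 = 6.05 h.
- Fall in Group A: (1 − 0.7) × 1.35 ≈ 0.4 h.
- Group B's before value is month 3, which is not gated, so its fall is about 0. Over 24 patients: (12 × 0.4 + 12 × 0)/24 = 0.2 h.

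**Range of the Group A fall.** It is 0.18 h at SD 1.5 h and 0.29 h at SD 2.0 h. At SD 2.5 h it is 0.14 to 0.68 h for correlations from 0.9 down to 0.5. If 5.1 h is read as the mean after the gate, it is 0.42 h (SD 1.5 h) to 0.86 h (SD 2.0 h).

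**Fall in Kinesia.** This equals (same-visit minus across-visit correlation with the diary) × 1.35 h. The documents give neither correlation. Assume a correlation of 0.9 between the patients' underlying levels on the two instruments, and a same-visit error correlation of 0 or 0.5.
- Error correlation 0: both correlations are 0.7 × 0.9 = 0.63, so the fall is 0.
- Error correlation 0.5: 0.63 + 0.3 × 0.5 = 0.78 against 0.63, so the fall is 0.15 × 1.35 = 0.20 h.

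That is 0 to 0.20 h in Group A and 0 to 0.10 h over all 24.

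**Effect on the choice.** Trials of 12 + 12 patients were simulated with two instruments of identical mean, SD, retest correlation and true effect. The table shows how often the diary had the larger standardised effect.

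| Contrast and scenario | Diary chosen |
|---|---|
| Before-after, no gate | about 50% |
| Before-after, gate, true effect 2 h, SD 2.5 h | 60–63% |
| Same, SD 1.5–2.0 h | 57–59% |
| Before-after, gate, no true effect | 60–65% |
| Group A versus B, change from baseline | 52–54% |
| Within-patient rifaximin minus placebo | about 52% |

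**Why the crossover contrast removes the tilt.** For Group A it is (baseline − month 1) − (month 3 − month 4). For Group B it is (month 3 − month 4) − (baseline − month 1). The 0.4 h gate fall enters as +0.4 in A and −0.4 in B, so it averages to 0. A reporting response that is equal in both periods cancels within each patient.

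**When the instruments differ.** With the gate only and Kinesia's error SD set 25% lower, Kinesia was correctly chosen in 72–82% of trials by before-after, 68–75% by Group A versus B, and 74–82% by the crossover contrast.

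**The case against.** The strongest reply is that the protocol nowhere says before-after for this endpoint. It says within-patient, which could mean pairing the two instruments in the same patient, or a rifaximin-versus-placebo contrast from the crossover. That stands as a point about wording. But an effect size needs a contrast, and before versus after rifaximin is the only within-subject contrast the plan defines. On the kindest reading the rule is undefined and still needs text.

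The planners will also have a placebo-controlled result for each instrument, since both are primary measures under the between-subjects analysis, and the SAP regards that analysis as the sounder guide to a later controlled trial. So a reader should not infer that the next trial is bound to rest on an effect that disappears against placebo. What remains is that secondary endpoint 2 does not tie the selection to that analysis.

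A reader might also infer that the diary is almost certain to win. With an assumed diary-only response of 0.5 h it is chosen in about 84% of simulated trials, and with 1.0 h in 94 to 97%. The documents contain no such response and no Kinesia SD, and do not say that Kinesia is unaffected by placebo. These figures are illustrative only.

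The section on potential pitfalls expects participants well above the cutoff, which would reduce regression to the mean. The planning mean is, however, only 5.1 − 4 = 1.1 h above it.

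Finally, replacing before-after by a 12 v 12 comparison alone would lose precision and, for the gate alone, choose the better instrument slightly less often. That objection stands and shapes the fix.

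**Conclusion.** The concern holds in a limited form. Followed as written, with within-patient read as the only contrast the plan defines, the selection rule leans towards the diary for a reason unrelated to sensitivity. The part that can be sized from the documents is modest: a net 0.1 to 0.2 h over 24 patients against a planned effect of 2 h, and a diary selection rate of about 57 to 64% between equal instruments. It rests on normality, equal SDs for the two instruments, the plan's correlation of 0.7 and assumed between-instrument correlations. The direction was the same in every gated before-after scenario run. Any differential placebo response would add to the tilt by an amount the documents do not allow one to state. The primary inference of this trial is not affected; what is affected is the choice of primary endpoint for the larger one.

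**What to change.** Reword secondary endpoint 2 and add its method to the statistical analysis plan section, for example:

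> *The diary and Kinesia 360 will be compared on the standardised placebo-controlled effect: each patient's rifaximin-period change minus placebo-period change, averaged with equal weight over the two sequences and divided by the pooled within-sequence SD. A bootstrap interval, resampling patients within sequence, will be given for the difference between instruments. The Group A versus Group B difference in change from baseline at 1 and 3 months will be reported alongside as a check free of carryover. Before-after effect sizes will be descriptive and will not be used to select the future primary endpoint.*

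State in advance what sensitivity means; the standardised effect above could serve for both terms.

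The cost is SAP text and one additional analysis of data already planned. There are two downsides. The crossover contrast assumes little carryover from Group A's rifaximin into its placebo period, and the protocol itself treats the duration of benefit as something still to be estimated. The 12 v 12 check avoids that assumption but is less precise and may show no clear winner, which would be a legitimate pilot result.

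### The 24-patient paired t-test has power for an uncontrolled before-after change, not for a rifaximin effect, and the crossover's within-patient drug-versus-placebo contrast is not planned

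*Combined protocol and SAP*

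**What the plan says.** All of this is in the section Randomization, Sample Size Estimation and Statistical Analysis Plan, unless another heading is named.

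- The first primary analysis is uncontrolled: "A within-subjects comparison (paired t-test) will compare all subjects (n=24) before and after rifaximin treatment". For Group A it compares baseline with months 1 and 3. For Group B it compares "3 months (end of placebo treatment, and baseline for rifaximin treatment) versus 4 months, and 3 months versus 6 months".
- Its power is given as 99.8% for 2 h and 95.3% for 1.5 h, using "a conservative estimate of standard deviation of 2.5 hours" and a before-after correlation of 0.7.
- The second primary analysis is a two-sample t-test of Groups A and B (12 each) at months 1 and 3. Its power for 2 h is 87.7% at SD 1.5 h and 64.9% at SD 2.0 h.
- The plan describes the pair as "one analysis with greater power to detect a treatment effect" and "a second analysis with greater validity for designing a future placebo-controlled trial".
- It concedes of the two-sample test that "it is possible that this analysis will not have the power to detect a treatment difference between groups", and closes with the assurance that "the within-subjects analysis described above should have ample power to detect a treatment effect".

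Under Study Plan and Blinding, the trial is a double-blind crossover. Group A takes rifaximin then placebo, Group B the reverse, with visits at baseline and months 1, 3, 4 and 6. Diary off time must average at least 4 h a day at baseline for a patient to be enrolled.

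**The concern.** The paired test uses only the visits around the rifaximin course, and no placebo course serves as its comparator. A fall in off time after rifaximin is the drug effect only if nothing else would have lowered off time. Three other causes are plausible here: placebo response on a patient-kept diary, a trend over time, and regression to the mean because patients are selected on a high baseline value of the same outcome. Blinding gives no protection, because this test never sets the two blinded treatments against each other.

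The plan nevertheless presents the test as the one with power for a treatment effect, at exactly the point where it admits that the controlled test may fall short. A significant paired result beside a null controlled result could then be read as evidence of efficacy in the application for the larger trial that this pilot is meant to support. Meanwhile Group A's placebo-period visits (months 4 and 6) enter neither primary analysis.

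**Working it through.** **Inputs from the plan:** n = 24 (12 per group); SD 2.5 h and correlation 0.7 for the paired test; mean off time 5.1 h; effects of 2 h and 1.5 h; entry threshold 4 h. **Assumed:** two-sided alpha 0.05 (not stated, but it reproduces all four stated powers); equal correlation between all visits; non-drug falls of 0.5 and 1.0 h.

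**1. The plan's own figures (noncentral t).** SD of the paired difference = 2.5 × √(2 × (1 − 0.7)) = 1.936 h. SE = 1.936/√24 = 0.395 h. With 23 df, power is 99.8% for 2 h and 95.3% for 1.5 h, as stated. The two-sample test with 22 df gives 87.7% and 64.9% at SD 1.5 and 2.0 h, also as stated. The arithmetic is right; what matters is which quantity the paired power refers to.

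**2. What the paired test estimates if rifaximin equals placebo.** Let each course be followed by a non-drug fall of m hours.
- If the fall has gone by month 3, both groups show m at month 1 and nothing at month 3.
- If it persists at the same level, Group A shows m. Group B shows 0, because its month 3 starting value already contains the fall. The average is m/2 at both time points.

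**3. Regression to the mean from the entry rule.** Take 5.1 h as the unselected mean. With a = (4 − 5.1)/2.5 = −0.44, the enrolled mean is 5.1 + 2.5 × φ(a)/(1 − Φ(a)) = 6.45 h. Group A is then expected to fall by 0.3 × (6.45 − 5.1) = 0.41 h without any treatment. Group B starts from month 3, not from the selecting diary, so the average over both groups is about 0.20 h. If 5.1 h is instead the enrolled mean, as the power statements use it, this model adds no such shift.

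**4. False improvement rate of the paired test** (simulation, at least 20,000 trials per scenario, SD 2.5 h, correlation 0.7, nominal 2.5% in the improvement direction; paired entries are for m = 0.5 / 1.0 h):

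| Scenario | Month | No truncation | 4 h rule applied, unselected mean 5.1 h |
|---|---|---|---|
| No non-drug response | 1 and 3 | about 2.5% | about 7% |
| Response persists | 1 and 3 | 8-9% / 21% | 18-19% / 36% |
| Response gone by month 3 | 1 | 23% / 68% | 41% / 84% |
| Response gone by month 3 | 3 | about 2.5% | about 7% |

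At smaller SDs the entry rule alone gives 5.6% (SD 1.5 h) and just over 6% (SD 2.0 h). The first-period A-versus-B test and the crossover contrast below stay near 2.5% throughout.

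**5. The contrast that is missing.** For each patient take month 1 minus month 4. In Group A this is rifaximin minus placebo plus a period effect; in Group B it is placebo minus rifaximin plus the same period effect. Half the difference in group means is the period-adjusted drug effect. Its SE is ½ × 1.936 × √(1/12 + 1/12) = 0.395 h. Power without carry-over:

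| Completers | Correlation | 2 h | 1.5 h |
|---|---|---|---|
| 24 (22 df) | 0.7 | 99.8% | 95.2% |
| 24 (22 df) | 0.5 | 96.3% | 80.2% |
| 18 (16 df, assumed) | 0.7 | 98% | 87% |
| 18 (16 df, assumed) | 0.5 | 89% | 67% |

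If c hours of Group A's benefit remain in its placebo period, a 2 h effect appears as 2 − c/2: 1.5 h if half persists, 1 h if all does. For 1 h, power with 24 completers is 67.7% at correlation 0.7 and 46.6% at 0.5.

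**The case against.** The strongest defence is that the plan already separates the two roles. It contrasts power with validity, admits that the controlled test may be underpowered, and says of the controlled test that "these data will provide valuable estimates of mean and standard deviation which can be used" for the later trial. It describes the paired test openly as before versus after and sets no rule that a significant paired result establishes efficacy. This is a pilot. All of that stands, and it confines the fault to how the paired test is described and what is inferred from it.

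Omitting a crossover contrast is also defensible. The pilot sets out to estimate how long benefit lasts, so carry-over cannot be presumed absent, and a first-period comparison is a recognised answer to it. The contrast is therefore a useful addition, not a required correction.

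Three stronger readings are tempting but not supported.
- A reader might infer that no planned analysis of all 24 patients can separate drug effect from placebo response. The 12-versus-12 comparison uses all 24 and does so.
- A reader might take 68% or 84% as the error rate of the paired analysis. Those figures apply only to month 1, only with an assumed 1.0 h response that has gone by month 3. In that case the month 3 paired test stays at about 2.5% or 7%.
- A reader might infer that the entry rule by itself badly inflates error. It gives about 5.6-7% on one reading of the 5.1 h mean and no inflation on the other.

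That the two power statements use different SDs is a separate matter and is not relied on here.

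**Conclusion.** The point holds in limited form and should be fixed. The 99.8% and 95.3% are correct for a before-after change and wrong as a description of power for a treatment effect. The test cannot stand in for the controlled comparison if that comparison proves underpowered.

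How far the paired test misleads depends on a placebo response that the documents do not give. For assumed lasting responses of 0.5 and 1.0 h, the false improvement rate is 8-9% and 21% without truncation, or 18-19% and 36% with it, at both time points. These rates rest on SD 2.5 h, equal correlation of 0.7 and normally distributed off time. With no placebo response or time trend, and 5.1 h as the enrolled mean, there is no inflation. The trial keeps a valid placebo-controlled primary; what it lacks is the within-patient contrast that its crossover design makes possible.

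**What to change.** 1. Label the paired before-after test descriptive and uncontrolled. Where the plan says "one analysis with greater power to detect a treatment effect" and "the within-subjects analysis described above should have ample power to detect a treatment effect", refer instead to power to detect a before-after change.
2. Add a supplementary crossover contrast. Compare Groups A and B on each patient's off time at month 1 minus month 4 (and month 3 minus month 6) by a two-sample t-test, and report half the difference in means as the period-adjusted rifaximin-minus-placebo effect. A mixed model with treatment, period, sequence and a random patient effect gives the same result when data are complete. State its power as conditional on no carry-over and on the number of completers, since the plan expects early drop-outs and rules out imputation.
3. Keep the first-period A-versus-B test as the carry-over-free controlled analysis, and take the effect size from it if benefit may last beyond 3 months.

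The cost is wording and a little more analysis, with no new visits. The drawback is that carry-over biases the added contrast toward zero, so it supplements the first-period test and does not replace it.

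### The between-group t-test on 'off' time at follow-up ignores the baseline diary. Baseline-adjusted ANCOVA and one common set of SDs would cost almost nothing.

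*Combined protocol and SAP*

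**What the plan says.** All of this is in the combined protocol and SAP, under Randomization, Sample Size Estimation and Statistical Analysis Plan.

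- **Outcome.** The primary outcome is named as change in 'off' time, to be analysed by a paired t-test in all 24 subjects and a two-sample t-test of 12 against 12.
- **SD from earlier data.** The plan cites one earlier study for a range of about 1.5 to 2 h.
- **Paired test.** Power is 99.8% for a 2 h difference and 95.3% for 1.5 h. The inputs are "a conservative estimate of standard deviation of 2.5 hours" and "a moderate correlation of 0.7 between the measurements before and after treatment".
- **Between-group test.** "We will use a two-sample t-test to compare the “off” time between groups A and B at 1 month and 3 months past baseline". The assumed effect is "a decrease in “off” time of 2 hours in the rifaximin group, and no change in the placebo group". On that basis, "we will have 87.7% power or 64.9% power to detect the difference between groups based on standard deviations of 1.5 and 2.0 hours". Neither the 2.5 h SD nor the correlation enters this calculation.
- **Caveat.** The plan adds that its SD estimates are imprecise, that the between-group test may therefore lack power, and that the data will still give means and SDs for a larger trial.

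Under Study Plan and PD Diary, every subject completes a three-day diary before the baseline visit, and again before each later visit.

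**The concern.** The between-group test is the only randomized, placebo-controlled comparison in the analysis plan; the paired test is before-after on rifaximin. The plan itself regards the between-group analysis as the more valid guide to a future controlled trial. Two features weaken it.

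First, as described, it compares follow-up values and leaves out the baseline diary. If the correlation is 0.7, as the plan assumes, baseline accounts for 0.7² = 49% of the variance at follow-up. With 12 per group, that is a large amount of precision to leave unused. The description also fits poorly with an outcome defined as change.

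Second, the two power calculations concern the same variable in the same patients but use different SDs, and no reason is given. The cautious SD appears where power stays above 95% anyway. It does not appear where it would change the picture.

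At stake are the precision of the controlled estimate and how a null between-group result is read.

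**Working it through.** **Inputs from the plan.** 12 per group; 2 h difference; SDs of 1.5, 2.0 and 2.5 h; r = 0.7; 24 pairs. Alpha and sidedness are not stated. Two-sided 0.05 is assumed because it reproduces all four stated powers (exact noncentral t). A one-sided test does not: it gives 93.6% and 76.7% at SD 1.5 and 2.0.

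**1. Reproduce the paired figures.** SD of the difference = 2.5 × √(2 × (1 − 0.7)) = 1.94 h. Noncentrality = difference ÷ (1.94/√24), 23 df.
- 2 h: 5.06, power 99.8% (as stated).
- 1.5 h: 3.79, power 95.3% (as stated).

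If 2.5 h were the SD of the difference, the powers would be 96.3% and 80.4%, which do not match. So 2.5 h is the SD of a single 'off'-time measurement, the quantity that a two-sample test of follow-up values needs.

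**2. Reproduce and extend the between-group figures.** Noncentrality = 2 ÷ (SD × √(2/12)), 22 df.
- SD 1.5: 3.27, power 87.7% (as stated).
- SD 2.0: 2.45, power 64.9% (as stated).
- SD 2.5: 1.96, power 46.6% (not in the plan).

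**3. If change scores are compared.** SD of change = SD × √(2(1 − r)). At r = 0.7 this is 1.94 h for SD 2.5 and 1.55 h for SD 2.0, with powers of 67.7% and 85.6%. At r = 0.5 the factor is 1, so power equals that of the follow-up test. Below r = 0.5, change scores do worse than follow-up values.

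**4. ANCOVA on baseline.** Residual SD = SD × √(1 − r²), 21 df. The variance of the adjusted group difference is residual SD² × (2/12 + D²/S), where D is the chance difference in baseline means and S the pooled within-group sum of squares of baseline. Ignoring D gives 74.4% (SD 2.5) and 90.5% (SD 2.0) at r = 0.7. Averaging over simulated normal baselines for 12 v 12, which inflates the variance by about 5%, gives:

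| | SD 2.5 h | SD 2.0 h |
|---|---|---|
| t-test on follow-up values | 46.6% | 64.9% |
| ANCOVA, r = 0.7 | about 72% | about 89% |
| ANCOVA, r = 0.5 | about 56 to 57% | about 75% |
| ANCOVA, r = 0.3 | about 48% | about 67% |
| ANCOVA, r = 0 | about 45% | about 63% |

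The values r = 0.5, 0.3 and 0 are assumptions made to show the range; the plan gives only 0.7. The last row is the cost if baseline carried no information: about 2 percentage points.

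**The case against.** Several points on the other side stand.

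- **The stated powers are correct.** 87.7% and 64.9% are exact for the SDs printed with them, and those SDs are both ends of the plan's cited range. The 2.5 h value is a margin above that range. Whether 1.5 to 2 h is right cannot be checked without the cited study.
- **The plan already warns the reader.** It prints a power below 65%, says this comparison may fail to detect a difference, and presents the study as a pilot for estimating means and SDs.
- **An unadjusted t-test is valid.** In a randomized comparison, adjustment for baseline improves efficiency; it does not repair a biased test.
- **The 0.7 has no source.** Entry requires at least 4 h of 'off' time, against an assumed mean of 5.1 h. Cutting off the lower end of the baseline distribution may reduce the correlation. The gain must therefore be given as a range.

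A reader might infer that the stated power is too favourable and that the true figure is 46.6%. The documents do not support that. The 46.6% takes the cautious SD without the correlation the plan pairs it with, and applies only to follow-up values. On the change-score reading, which the named outcome allows, power at SD 2.5 and r = 0.7 is 67.7%, inside the stated range. Nor is there any sign that the less favourable figure was held back on purpose.

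These points leave two gaps: the caveat gives no figure at 2.5 h, and it does not explain why the two calculations use different SDs.

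**Conclusion.** The point holds as an inexpensive improvement and a reporting gap. It is not an arithmetic error. As described, the between-group test leaves the baseline diary unused. ANCOVA would raise power for a 2 h difference from 46.6% to about 72% at SD 2.5, and from 64.9% to about 89% at SD 2.0, if the plan's r = 0.7 is right. At r = 0.3 the gain is only about 2 points. For positive r below 1, the residual variance factor 1 − r² is smaller than both the follow-up factor of 1 and the change-score factor of 2(1 − r). Before the small loss for estimating the slope, ANCOVA therefore does better than either alternative.

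Separately, the SD of 2.5 h should appear in both calculations, and the plan should settle whether follow-up values or changes are compared.

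The figures assume two-sided 0.05, 12 per group with complete data, normal outcomes, equal SDs before and after treatment, and no change on placebo.

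**What to change.** 1. Replace the two-sample t-test with ANCOVA of month-1 'off' time on treatment group, adjusted for baseline 'off' time, and the same model at month 3. This also settles whether follow-up values or change scores are analysed, since with baseline as covariate both give the same treatment estimate.
2. Use SDs of 1.5, 2.0 and 2.5 h in both power calculations, and state alpha and sidedness.
3. Add the SD 2.5 figure for the unadjusted comparison: 46.6% for follow-up values, or 67.7% for change scores at r = 0.7.
4. Give ANCOVA power over r, for example 0.3, 0.5 and 0.7, allowing for chance baseline imbalance. At SD 2.5 this is about 48%, 56 to 57% and 72%. Do not quote the r = 0.7 figure alone.

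The cost is one degree of freedom (21 instead of 22), a few lines of SAP text and one less favourable printed figure. No new data, visits or subjects are needed.
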